## ABBREVIATIONS

CBS	Corticobasal syndrome
CSI-SF	Client Satisfaction Inventory – Short Form
CURE-PSP	CurePSP Foundation, supporting research and patient outreach for individuals with Progressive Supranuclear Palsy and related prime-of-life neurodegenerative disorders
DLB	Dementia with Lewy Bodies
ED	Emergency Department
EQ5D	Euro-Qol 5D – instrument for measuring quality of life
HRQOL	Health-Related Quality of Life
HY	Hoehn and Yahr Scale
HVP	Home Visit Program
MCSI	Multidimensional Caregiver Strain Index
MoCA	Montreal Cognitive Assessment
MSA	Multiple System Atrophy
PD	Parkinson's Disease
PDD	Parkinson's Disease Dementia
PDQ-39	Parkinson's Disease Questionnaire
PDQ-8	Parkinson's Disease Questionnaire – Short Form
PHI	Personal History Information
PI	Principal Investigator
PRD	Progressive Supranuclear Palsy and Related Disorders
PSP	Progressive Supranuclear Palsy
REDCap	Research Electronic Data Capture
UPDRS	Unified Parkinson's Disease Rating Scale

## I. Project Rationale and Description

### I.a. Purpose of the Study

The aim of this study is to test whether and to what degree an interdisciplinary home visit program will improve patient- and caregiver-reported outcomes and healthcare utilization when compared with usual care, and to identify unmet needs in this population. Evidence supports interdisciplinary and home-based models of care in other elderly populations, however no such models have been studied in people with PRD. Improving access to comprehensive, specialized, in-home patient care and caregiver support offers the potential to minimize the downward spiral of morbidity and preventable healthcare utilization.

Our objective is to expand the reach of comprehensive clinical care and research studies to homebound patients with PRD through an interdisciplinary home visit program bringing medical, nursing, and social work expertise directly to patients and caregivers. We hypothesize: 1) Home visit program subjects will show improved quality of life from the time of enrollment, to 1-year follow-up and will have better quality of life at 1 year compared with controls, as measured by change in EuroQoL-5 scores, respectively; 2) Program caregivers will show less deterioration in caregiver strain from enrollment to 1-year follow-up and will have lower strain at 1 year compared with controls, as measured by change in Multidimensional Caregiver Strain Index, respectively; and 3) Participants will express multiple unmet needs in several domains, including: education and resources for rare diagnoses, treatment of non-motor symptoms, palliative care, and end-of-life planning.

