The study team will provide one scheduled follow-up call at about 4 weeks post-visit (though this call

may occur as early as 2 or as late as 8 weeks after each visit, depending on the individual subject's circumstances and the ability of the study team to reach the patient and/or caregiver by phone). Change in quality of life and caregiver strain will be assessed over one year. The home visit cohort will be compared to a "usual care" cohort as measured by individuals with PRD living in the community who complete the online survey annually for 2 years covering demographics, disease history, quality of life, and caregiver strain.

Sixty (60) control participants will be recruited from the Rush University Parkinson's Disease and Movement Disorders Program, NYU Parkinson's Disease and Movement Disorders Institute, CurePSP (via social media postings), and from the CurePSP network of support group participants via in-person presentations from study staff, printed fliers, and emails. Control participants will be invited to complete an online version of the survey, created using REDCap research electronic data capture technology (HIPAA-secure database) housed at NYU. Caregivers of controls, when available, will also be invited to complete the online survey.

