##### II.d. Racial and Ethnic Origin

There will be no exclusion of subjects based on racial or ethnic characteristics. Study demographics are expected to match those of the population from which it was drawn. However, subjects must be fluent in English to participate in the Home Visit Program due to the general lack of appropriately translated

neurological and neuropsychological assessments and appropriate normative comparison samples. These factors are critical for accurate administration, scoring, and interpretation of neurological and neuropsychological test data.

II.e. Inclusion Criteria for All Subjects:

1. Each subject must be 40 years of age or older. A subject may be of either gender, any race/ethnicity.
2. Subjects will be those diagnosed with progressive supranuclear palsy, multiple system atrophy, corticobasal syndrome, Dementia with Lewy Bodies (DLB), or atypical parkinsonism without mention of idiopathic Parkinson's disease.
3. English speaking.

a. **Additional Inclusion Criteria For Home Visit Arm:**

- i. Each subject must *either* 1) be willing and able to provide written, informed consent for the study, and for whom capacity to consent will be assessed using the "Additional Inclusion Criteria for Home Visit Arm" document, or 2) if unable to provide informed consent due to lack of capacity, a caregiver is able to provide informed consent *and* the subject provides assent to participation.
- ii. Subjects must be homebound according to the Medicare definition: "Leaving your home isn't recommended because of your condition; your condition keeps you from leaving home without help (such as using a wheelchair or walker, needing special transportation, or getting help from another person); leaving home takes a considerable and taxing effort." (<http://www.medicare.gov/pubs/pdf/10969.pdf>)
- iii. Subjects reside in Chicago at the time of Visit 1.
- iv. The Subject must reside independently at the time of Visit 1.
- v. Subjects have one or more of the following criteria:
  - Fluctuation
  - Multi-morbidity
  - Mismanages medication
  - Cognitive impairment
  - Symptoms of depression and/or anxiety
  - High risk for re-hospitalization
  - High risk for nursing facility admission
  - Suspected elder abuse
  - Recent history of increased falls in home
  - Caregiver burnout suspected
- vi. Ability to participate in the research study as deemed by the Principal Investigator.

b. **Additional Inclusion Criteria for Usual Care Arm:**

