Data management: The primary data will be entered into a HIPAA-compliant database (**REDCap**), with quarterly audits for fidelity. Data will be exported to Stata 14 for analysis.

Data analysis:

Descriptive statistics. We will describe the demographics, disease characteristics, QoL, and caregiver strain at baseline in patients and caregivers. Categorical variables will be summarized by frequencies and percentages. Continuous variables will be assessed for normality and summarized by mean and standard deviation, or median and interquartile range. Adequacy of matching will be evaluated using chi-square and *t*-tests.

Bivariate analyses. Change in EQ5D subscores and VAS over 1 year will be compared between groups, stratified by diagnosis, by two-sample *t*-test or nonparametric Wilcoxon rank sum test. If a subject dies or is lost to follow-up, the last values of the EQ5D will be carried forward. We will analyze the association with change in EQ5D for each demographic, confounder, and covariate via chi square or multivariate ANOVA, as appropriate. We will compare change in MCSI over 1 year by group, stratified by diagnosis; if lost to follow-up, the last MCSI value will be carried forward.

Multivariable analyses. We will construct a linear regression model with change in EQ5D domains and VAS as sequential dependent variables, and treatment status as the primary independent variable, stratifying by diagnosis. We will build complex models to assess the contributions of each significant covariate. Model building will include manual stepwise, backward elimination checking for multicollinearity and confounding. We will construct similar models wherein MCSI change is the dependent variable.

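### The first half of hypothesis 1 predicts absolute improvement in the home-visit arm, but the SAP names only between-group tests of change and its sample size matches a one-sample calculation

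*Protocol*

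**What the plan says.** Protocol I.a gives hypothesis 1 in two halves. The first is that "Home visit program subjects will show improved quality of life from the time of enrollment, to 1-year follow-up". The second is that these subjects "will have better quality of life at 1 year compared with controls, as measured by change in EuroQoL-5 scores". Hypothesis 2 opens differently: "Program caregivers will show less deterioration in caregiver strain from enrollment to 1-year follow-up". Its second half predicts lower strain than controls at one year, again with change in the MCSI as the measure. The overall aim in the same section is comparative: to test whether the program "will improve patient- and caregiver-reported outcomes and healthcare utilization when compared with usual care".

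On analysis, Protocol I.c says: "Change in quality of life and caregiver strain will be assessed over one year". The SAP (Primary outcomes) likewise says that change from baseline to one year will be assessed in each EQ5D domain and the VAS. Neither statement names a within-arm analysis.

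The treatment analyses that are named are in the SAP. Under Bivariate analyses: "Change in EQ5D subscores and VAS over 1 year will be compared between groups, stratified by diagnosis", by two-sample t-test or Wilcoxon rank sum test. Under Multivariable analyses, change is regressed on treatment status. The MCSI is handled in the same way. The SAP specifies no paired or one-sample analysis of the home-visit arm and no comparison of one-year levels.

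The SAP's Power calculation expects 17 home-visit patients and 80 control patients at 12 months. For a VAS difference of 6.5-8.0 points, with SD 18, power 0.80 and two-sided alpha 0.05, it states a requirement of 42-63 patients.

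**The concern.** The first half of hypothesis 1 can be true or false whatever happens to controls. The planned tests concern only the difference from controls. The two can therefore disagree, and the plan does not say which one settles the hypothesis.

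This matters in two directions. These are progressive disorders, so a useful program might slow decline without raising scores. Such a program would serve the comparative aim and could succeed on the planned test, yet contradict the first half of hypothesis 1. Conversely, a rise within the home-visit arm, which has no comparator, could be reported as support even if the between-group comparison showed nothing. Hypothesis 2 avoids this by speaking of less deterioration.

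The second half adds an ambiguity, because it refers to quality of life at one year but measures it by change. The distinction has consequences: home-visit subjects must be homebound (Protocol II.e: "Subjects must be homebound according to the Medicare definition"), and the usual-care criteria contain no such requirement. The arms may therefore start at different levels.

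**Working it through.** **1. Reproducing the SAP's 42-63 patients.** Inputs, all from the SAP: difference d = 6.5 or 8.0, SD 18, power 0.80, two-sided alpha 0.05 (1.960 + 0.842 = 2.802).

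| Calculation | d = 8.0 | d = 6.5 |
|---|---|---|
| One-sample, normal: (2.802 × 18 / d)² | 39.7, so 40 | 60.2, so 61 |
| One-sample or paired t-test | 41.7, so **42** | 62.1, so **63** |
| Two-sample, normal, per arm: 2 × (2.802 × 18 / d)² | 80 | 121 |
| Two-sample t-test, 1:1, per arm | 80.4, so 81 | 121.3, so 122 |

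The one-sample t-test gives the SAP's range exactly. At the stated SD, the two-sample test does not. A one-sided two-sample calculation gives 63 and 95 per arm, which does not match either. A two-sample calculation would come close only with an SD of change near 18/√2 = 12.7 (40 and 61 per arm by the normal formula), and the SAP states no such SD.

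**2. Power at the SAP's expected completers.** The SD of change is not given; 18 is assumed, which corresponds to a within-person correlation of 0.5.

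- Within-arm, n = 17: 95% CI half-width = 2.120 × 18/√17 = 9.25 points; power 0.29 (d = 6.5) to 0.41 (d = 8.0).
- Between groups, 17 against 80: standard error = 18 × √(1/17 + 1/80) = 4.81; power 0.27 to 0.38.

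With SD of change = 18 × √(2(1 − r)) and r from 0.3 to 0.7 (SD 21.3 to 13.9), within-arm power is 0.22-0.44 for d = 6.5 and 0.31-0.60 for d = 8.0. Between-group power is 0.20-0.41 and 0.29-0.57. These figures ignore the stratification by diagnosis.

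**3. How far the first half and the planned test can diverge.** Take a benefit of 8.0 points and let the control change vary. The control changes are assumptions; neither document gives an EQ5D decline rate. SD of change is 18, with 17 against 80 patients.

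| Control change | Home-visit change | Chance of a significant favourable between-group result | Chance of a significant within-arm rise |
|---|---|---|---|
| 0 | +8 | 0.38 | 0.41 |
| −8 | 0 | 0.38 | 0.025 |
| −10 | −2 | 0.38 | 0.008 |
| −12 | −4 | 0.38 | 0.002 |

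The between-group column depends only on the 8-point difference. The within-arm column falls as the assumed decline grows. If controls fall by 5, the home-visit arm rises by 8 − 5 = 3, and the first half of the hypothesis is true. It becomes false once decline without the program reaches or exceeds the benefit.

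**4. Level against change in the second half.** The one-year level difference is the benefit in change minus the baseline deficit of the home-visit arm (assumed). For an 8-point benefit, deficits of 0, 4, 8 and 12 give level differences of +8, +4, 0 and −4. The two readings agree only if the arms start equal.

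**The case against.** The strongest reply is that the SAP already contains the right test. A between-group comparison of change would credit slowed decline, and it matches the comparative aim in Protocol I.a. That stands: the fault lies in the wording of the first half of hypothesis 1 and not in the SAP's choice of test.

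A reader might infer that the SAP analyses neither half of hypothesis 1. The documents do not support that. The sentence on the second half goes on to name change in EQ5D scores as the measure, and on that reading the SAP tests it directly. What remains is an ambiguity to clear up.

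A reader might also infer that absolute improvement is unattainable. The documents do not show this. Protocol IV.b gives a route to improvement, through detection and treatment of unsuspected depression, anxiety or cognitive disorders, and a hypothesis is allowed to be ambitious. Whether the first half fails depends on a decline rate that the documents do not give.

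Nor does low power argue for one target over the other, since the two tests have similar power under the same assumptions. The case for the between-group contrast is that it has a comparator and fits the aim.

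Finally, Protocol II.a calls the study exploratory and says that no power analysis was done. That lowers the weight of the point. It does not remove the inconsistency, because the SAP lists the EQ5D and MCSI as primary outcomes and prints a sample-size requirement.

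**Conclusion.** The point holds in a limited form. The first half of hypothesis 1 claims within-arm improvement, for which no analysis is named. The named tests are between-group, and the 42-63 patients is a one-sample figure at the stated SD of 18. These three elements do not share one target. The planned two-sample test would need about 81-122 patients per arm at that SD with equal arms, against 17 and 80 expected completers.

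The mismatch of targets follows from the documents alone. The size of any divergence does not: it depends on the assumed decline and on treating 18 as the SD of change. The example of controls falling 10 points and home-visit patients 2 (0.38 against 0.008) shows what could happen and is not a forecast.

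The stronger conclusion, that the SAP's analysis would make a useful program fail its own hypothesis, is not supported. The planned test is the one that would recognise such a program. The point should be corrected before analysis, but it is not a critical defect in a study described as exploratory.

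**What to change.** 1. Restate hypothesis 1 in Protocol I.a as: *home-visit patients will show a more favourable 1-year change in EQ5D than controls*.
2. State that the second halves of hypotheses 1 and 2 mean change and not level at one year.
3. In the SAP, make the between-group difference in one-year change the result that decides each hypothesis. For the EQ5D, say which of the five domains and the VAS this refers to; the VAS is the only one for which the SAP gives a sample size.
4. Report the within-arm mean change with its 95% CI, and the one-year means by arm, as descriptive results and not as evidence of effect.
5. Restate the sample-size sentence for the two-sample comparison. Say whether 18 is the SD of the score or of the change, and give the power at the expected numbers.

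The cost is wording in both documents, one descriptive table and a recalculated sentence. The planned inferential analysis does not change. The trial gives up the claim that patients improve in absolute terms, and the restated power will look low (0.27-0.38 at 17 against 80 if the SD of change is 18).

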### I.b. Background

Progressive supranuclear palsy affects approximately 20,000 people in the United States. Progressive supranuclear palsy and related disorders (PRD) are debilitating, costly, and understudied conditions that significantly impacts patient quality of life and caregiver strain. When patients with severe, neurodegenerative disease progress to the point that they can no longer access their usual care, their risk of hospitalization and institutionalization increases. Unfortunately, when these same patients are hospitalized or institutionalized, they suffer from excess morbidity and mortality compared with individuals without movement disorders. There is a tremendous unmet need to foster continuity of care for the sickest patients with neurologic disease.

The study of individuals with PSP, and how a medical home visit model of care can benefit them, is an essential component of our movement disorders research. This study will include information collected during routine patient care (e.g., demographics, medication history, and standard motor assessments), detailed data on medication reconciliation and medication errors, periodic in-home clinical assessments, neuropsychological questionnaires, patient satisfaction with the home visit program and components, and resource utilization data. The assessments conducted in the research provide crucial data towards the understanding of how medical home visits can improve patient and caregiver quality of life, and reduce hospital and nursing facility admissions, versus controls, who do not receive medical home visits.

### I.c. Study Design

The initial survey piloting of this study was already conducted at New York University (IRB approval date 3/1/2017, see uploaded IRB approval letter). Participants were recruited from the Fresco Institute at

NYU and contacted by the NYU study team to complete a cognitive interview in which the survey was administered and the participant answered the questions in real time, providing feedback on confusing, vague, or burdensome questions. We piloted the survey in 8 individuals, including both patients and caregivers.

In the home visit arm of the study, 25 individuals with PSP or PSP-related disorders living in Chicago and meeting Medicare "homebound" criteria will be recruited to the treatment (home visit) arm of the study. At the time of enrollment in the treatment (home visit) arm, clinical and demographic data about study subjects will be collected by study personnel, both directly from subjects and from retrospective medical chart review. Patients followed at the Rush Parkinson's Disease and Movement Disorders Program or followed elsewhere in Chicago who can provide medical records confirming their diagnosis of PRD, and who meet inclusion criteria for this study, will be offered the opportunity to participate by their treating neurologist at the time of or after their routine office visit (for individuals seen at Rush), or will be screened and contacted directly by the study team.

Subjects who are interested in participating will be given information about the study and the opportunity to ask questions about it in detail; those who opt to participate will be scheduled for an initial home visit (Visit 1), at which time, the verbal and written informed consent process will take place prior to completing any study activities.

Subjects who commence on study will receive four quarterly structured, interdisciplinary home visits over 12 months from a team comprised of a movement disorders neurologist, social worker and nurse. At Visit 1, the nurse, social worker, and a member of the research team will travel to the home. The neurologist will be present via telemedicine. The home visit team will travel with an iPad and, after obtaining informed consent, connect to the neurologist via HIPAA-secure videoconferencing and begin the protocol-driven clinical activities and assessments in Figure 1 in the uploaded protocol. The nurse will conduct and, with the neurologist, score the UPDRS Motor Examination, reconcile medications, and complete a standardized home safety assessment. The social worker will obtain demographics, and administer the Multidimensional Caregiver Strain Index (MCSI) to the caregiver and the EuroQoL-5D (EQ5D) to both the patient and caregiver, respectively. The social worker will conduct a needs assessment of the dyad, including a discussion of goals of care. The team will administer the same survey that the usual care subjects will complete as a structured interview, as individuals in the home visit arm are expected to have more difficulty with dexterity and potentially cognitive issues, limiting the feasibility of completing the online survey unassisted. The survey will cover demographics, disease history, comorbidities, healthcare utilization, and unmet needs of the patient and caregiver. The team will probe for further details on necessary services or resources, and will ask specifically about areas of need in: education, resources, non-motor symptoms, psychiatric and palliative care, spiritual and/or religious support, and end-of-life planning. The team will create and counsel the dyad on a care plan. Within the Rush electronic medical record, the neurologist will enter orders and send a comprehensive, template-based note to the patient's healthcare providers. Visits 2-4 will be conducted at 4-month intervals and are identical except the social worker may join by telemedicine, depending on availability, and the queries on unmet needs will only be repeated at Visit 4.

The visits may be performed where the subject is residing at the time of scheduled visit (which could include but not restricted to the subject's home, nursing facility, hospital, etc.). The duration of the visits will be approximately 2.5-3 hours for Visit 1 and 1.5-2 hours for Visits 2-4.

The study team will provide one scheduled follow-up call at about 4 weeks post-visit (though this call

may occur as early as 2 or as late as 8 weeks after each visit, depending on the individual subject's circumstances and the ability of the study team to reach the patient and/or caregiver by phone). Change in quality of life and caregiver strain will be assessed over one year. The home visit cohort will be compared to a "usual care" cohort as measured by individuals with PRD living in the community who complete the online survey annually for 2 years covering demographics, disease history, quality of life, and caregiver strain.

Sixty (60) control participants will be recruited from the Rush University Parkinson's Disease and Movement Disorders Program, NYU Parkinson's Disease and Movement Disorders Institute, CurePSP (via social media postings), and from the CurePSP network of support group participants via in-person presentations from study staff, printed fliers, and emails. Control participants will be invited to complete an online version of the survey, created using REDCap research electronic data capture technology (HIPAA-secure database) housed at NYU. Caregivers of controls, when available, will also be invited to complete the online survey.

